6.2.2 Weeks 1 to 6 - Intensive plasma exchange period

Full Plasma Exchange (Window range +/- 1 day)

Plasma samples will be collected from the subject before and 15-30 minutes after each procedure, to allow the pertinent tests. Additional plasma samples will be collected each time for storage at -70°C and possible future assays.

The following tests will be made before each procedure: biomarkers of AD (A β -40, A β -42, β -secretase, γ -secretase, cholesterol, LDL, HDL, VLDL, C-reactive protein, rheumatoid factor, IL-1b, IL-6, ferritin and TNF- α), coagulation factors (prothrombin time (Quick), aPPT, calcium and fibrinogen) and proteinogram (total proteins, albumin, α 1-globulina, α 2-globulina, β -globulina, γ -globulina and IgG). In addition, a cell count will be made including hematocrit, hemoglobin and erythrocytes, platelets and leukocytes (if an abnormal leukocyte count is recorded, it will be obligate to specify neutrophils, basophils, eosinophils, lymphocytes and monocytes). The samples obtained after plasma exchange will be used to evaluate the biomarkers of AD, cell count, platelets, coagulation factors (prothrombin time

(Quick), aPPT, calcium), proteinogram, fibrinogen and troponin, as well as other biochemistry parameters (AST, ALT, LDH and creatinine).

A maximum of six full plasma exchange sessions will be made during this period: one per week.

The subject will remain in the center throughout the procedure and then for as long as needed to ensure a safe return home, under conditions similar to before plasma exchange.

Before plasma exchange, a physical examination will be made, with the recording of any anomalies. Concomitant medication is also to be registered, together with any adverse event detected since the last visit or since the last plasma exchange session. The anxiety and restlessness tests, if necessary, will be performed before each plasma exchange process, and between 15-30 minutes after replacement. These tests will be carried out by the same patient supervisor.

Vital signs (axillary temperature, heart and respiration rate, and blood pressure) will be determined 15-30 minutes before replacement during and again 15-30 minutes after the procedure, and as often as considered opportune by the investigator.

Any adverse event during or after the procedure, will be recorded.

Control group

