7.2 SAFETY END POINTS

The primary criterion of safety will be the percentage of plasma exchanges (full and low volume exchanges, including the infusion of albumin and IVIG) associated with at least one adverse event that may be related to the study procedure (adverse reactions). In addition, consideration globally will be made of the percentage plasma exchanges (full and low-volume exchanges, including the infusion of albumin and IVIG) involving some adverse event, whether or not related to the procedure.

Vital signs (blood pressure, heart rate, respiration rate, and body temperature) will be recorded before, during and after each plasma exchange session, where required. Evaluation will also be made (where required) of the different laboratory test parameters (blood cell counts, platelet count, prothrombin time (Quick), fibrinogen, total proteins, and calcium).

During the treatment periods (before each plasma exchange) and on the days when there is no replacement, anxiety and restlessness tests will be made based on the Overt

	Title: Statistical Analysis Plan
	Project #: IG1002 AMBAR
	Version: Final 1.0 Effective Date: 31July2018
	Protocol Version: Version 5.0 Effective Date: Feb2018

Aggression Scale (OAS) and the Agitated Behavior Scale (ABS), whenever considered opportune.

According to the criterion of the investigator, all the clinically important changes in vital function, laboratory test parameters and neuroimaging findings will be evaluated. Any adverse events occurring following start of treatment will be counted as treatment emergent.

The analysis of tolerability will be based on description of the safety variables according to their nature.

The adverse reactions will be coded according to the adverse events classification of the World Health Organization (WHO) (MedDRA current version), and will be described by a synonym (Preferred Term) and the affected organ / system, the intensity, causality and seriousness.

The safety population will be used for all safety summaries unless otherwise noted. Summaries will be presented by treatment group and overall unless otherwise noted.

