7.2.1 Plasma Exchange

The percentage of plasma exchanges (full and low volume exchanges, including the infusion of albumin and IVIG) associated with at least one adverse event that may be related to the study procedure (adverse reactions) will be summarized. Only adverse events with an onset no later than 72 hours after the end of the plasma exchanges (including the infusion of albumin or IVIG) will be considered for this analysis.

Plasma exchanges (full and low volumes exchanges) will also be summarized by the following measures:

- Plasma exchange performed (yes/no)
- Duration of plasma exchange
- Plasma exchange completed (yes/no)

The reasons for not completing the plasma exchanges will be presented in a data listing.

For the full plasma exchanges, also the following measures will be summarized:

- Route to perform full plasma exchange (peripheral / central)
- Number of bottles of albumin used (calculated as numbers of bottles in this batch + all additional bottles).
- Plasma volume exchanged (ml)

	Title: Statistical Analysis Plan
	Project #: IG1002 AMBAR
	Version: Final 1.0 Effective Date: 31July2018
	Protocol Version: Version 5.0 Effective Date: Feb2018

- Volume RF infused (ml)

For the low volume plasma exchange, the following parameters will be summarized:

- Target plasma volume
- Target RF volume
- Type of RF used (20% HAS, Other)
- RF infused
- Plasma volume exchanged (calculated as $[(PPP_{\text{post weight}} - PPP_{\text{bag empty}}) / 1.027 \text{ g/ml}] \text{ ml}$ where $PPP_{\text{bag empty}} = 41.87\text{g}$)
- Number of bottles Albumin used

For the plasma exchange visits where IVIG are to be infused (1st and 2nd treatment arm, LVPE1, LVPE5, and LVPE9) the following parameters regarding the IVIG dosing will be summarized:

- IVIG infused (yes/no)
- Theoretical IVIG dose (g)
- Infused dose(g)
- Ratio infused dose /theoretical dose
- Number of bottles used

In addition, percentage of plasma exchanges associated with at least one adverse event will also be summarized whether or not related to the procedure and/or study drug.

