7.2.2 Adverse Events

All adverse events will be coded using the Medical Dictionary for Regulatory Activities (MedDRA). Summaries will be presented for all adverse events (overall and by severity), adverse events determined by the investigator to be treatment-related (overall and by severity), serious adverse events, and adverse events causing discontinuation from the study.

The incidence of adverse events will be summarized using descriptive statistics by system organ class and preferred term. Patients are counted only once in each system organ class category, and only once in each preferred term category. Treatment-related adverse event summaries will include adverse events with missing relationship to study drug. For the summaries by severity, patients are counted at the greatest severity. Adverse events missing the flag indicating serious will be excluded from the summary of serious adverse events. In summary tables, AEs will be counted as “Not Related” if the causality with the product was recorded as “Unrelated”; Events will be counted as “Related” if the causality with the product was recorded as “Possibly”, or “Probably,” or “Unlikely”, or if relationship is missing. For the analysis of adverse events, the relationship to the study

	Title: Statistical Analysis Plan
	Project #: IG1002 AMBAR
	Version: Final 1.0 Effective Date: 31July2018
	Protocol Version: Version 5.0 Effective Date: Feb2018

procedure will be used as given in the CRF, regardless of whether or not the adverse event has an onset within 72 hours after the end of the last plasma exchange.

The adverse events will be summarized as follows:

- All AEs by SOC and PT
- All AEs by SOC, PT, and severity
- All AEs by SOC, PT, and causality with product
- Related AEs by SOC and PT
- Related AEs by SOC, PT, and severity
- Related AEs by SOC, PT, and relationship (product, procedure, product + procedure)
- Related AEs by SOC, PT, and product (albumin 5%, albumin 20%, Flebogamma DIF 5%)
- All SAEs by SOC and PT
- Related SAEs by SOC and PT
- SAEs with a fatal outcome by SOC and PT

The relationship to the product will be derived from the most recent plasma exchange.

For AEs which are on the date of the plasma exchange, it is assumed that the AE is during/post exchange, i.e. the AE will be associated to this PE. For the 3 active treatment groups, the derivation of the product will be as follows:

- For FPE1 to FPE6, the product is albumin 5%

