- For LVPE 1, LVPE5, or LVPE 9, for the full albumin + IGIV and the half albumin + IVIG treatment arm, the product will be flebogamma DIF 5%
- For LVPE 1, LVPE5, or LVPE9, for the half albumin treatment arm, the product will be albumin 20%
- For all other LVPEs, the product will be albumin 20%.

The related adverse events and related serious adverse events will also be analyzed based on the number of FPEs, FPEs using central access, FPE using peripheral access, and LVPEs. For this analysis, only AEs with an onset time no longer than 72 hours after the end of the most recent plasma exchange will be considered. If the time of onset is missing, or the end time of the plasma exchange/infusion of albumin or IVIG is missing, the start date of the AE must be within 2 days after the date of the most recent plasma exchange. Adverse events with missing relationship will not be considered in this analysis. Each plasma exchange is counted only once in each SOC and only once in each. Adverse events will also be analyzed by product (albumin 5%, albumin 20%, Flebogamma DIF 5%) based on the number of plasma exchanges. The denominator for this analysis is the number of performed plasma exchanges with the specific products.

	Title: Statistical Analysis Plan
	Project #: IG1002 AMBAR
	Version: Final 1.0 Effective Date: 31July2018 Protocol Version: Version 5.0 Effective Date: Feb2018

Listings for deaths, serious adverse events, adverse events leading to discontinuation, MedDRA dictionary terms for adverse event descriptions, and adverse event preferred terms by patient number will be presented. Adverse events associated with plasma exchanges will also be presented.

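### The SAP's same-day rule can count an adverse event that began before an exchange as a reaction to that exchange, and can give it the wrong product in the by-product tables

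*SAP*

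**What the plan says.** SAP 7.2 sets the primary safety criterion: the percentage of plasma exchanges with at least one adverse event that may be related to the study procedure. SAP 7.2.1 adds the time limit: "Only adverse events with an onset no later than 72 hours after the end of the plasma exchanges" are considered. Neither section says how an event is linked to a particular exchange.

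The linking rules are in SAP 7.2.2. "The relationship to the product will be derived from the most recent plasma exchange", and then: "For AEs which are on the date of the plasma exchange, it is assumed that the AE is during/post exchange", so the event is associated with that exchange. Product follows from visit number. FPE1 to FPE6 are albumin 5%. "For LVPE 1, LVPE5, or LVPE 9, for the full albumin + IGIV and the half albumin + IVIG treatment arm", the product is Flebogamma DIF 5%. Every other LVPE, and every LVPE in the albumin-only arm, is albumin 20%.

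The per-exchange analysis in the same section repeats the 72-hour limit and gives a date-based fallback that begins: "If the time of onset is missing, or the end time of the plasma exchange". The fallback applies only when a time is missing, so the SAP expects onset times to be available. Protocol 9.1.1 also makes the timing of the event relative to administration part of the minimum AE record.

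Protocol 6.2.2 states: "Before plasma exchange, a physical examination will be made, with the recording of any anomalies". Protocol 6.2.4 requires the same before each plasmapheresis, and both sections require laboratory samples before each procedure.

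**The concern.** Each session opens with an examination and blood tests, so some abnormalities will first be seen on an exchange day but before the exchange. Protocol 5.2.2.6 expects anaemia after the early full exchanges and falling immunoglobulin levels, and Protocol 9.1.3 lists anaemia and coagulation disorders as expected effects of exchange. An investigator could reasonably mark such a finding as procedure-related. Under the same-day rule it is then treated as having occurred during or after a procedure that had not started.

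Two outputs are at stake. One is the primary safety percentage, which should count reactions during an exchange or within 72 hours of its end. The other is the set of by-product tables, where the event takes that day's product even if the only product given so far was a different one, or none.

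**Working it through.** The plan states no figure for this point, so there is none to reproduce. The check has four steps.

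**1. Does the 72-hour filter remove a pre-exchange onset?** The SAP test is: onset time minus end of exchange is at most 72 hours. An onset before the session starts gives a negative difference and passes. Protocol 8.3 words the window as running from completion or stopping of the infusion. The SAP wording sets no starting point.

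**2. Where would the event go if its recorded time were used?** It would go to the previous exchange, so the gap to that exchange decides the outcome. Nominal weeks and windows come from Protocol Appendix 8: FPE1–6 in weeks 1–6 (±1 day) and LVPE1–12 in weeks 9–53, every 4 weeks (±5 days). Shortest gap = nominal gap minus both windows.

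| Interval | Number | Nominal gap (days) | Shortest gap (days) |
|---|---|---|---|
| FPE to next FPE | 5 | 7 | 7 − 1 − 1 = 5 |
| FPE6 to LVPE1 | 1 | 21 | 21 − 1 − 5 = 15 |
| LVPE to next LVPE | 11 | 28 | 28 − 5 − 5 = 18 |

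The minimum over all 17 intervals is 5 days, about 120 hours, against a limit of 72. For exchanges within window, a correctly linked event leaves the criterion and does not move to another session. At FPE1 there is no previous exchange, so the event is pre-treatment. Each exchange counts at most once, so the same-day rule either adds a positive exchange or changes nothing.

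**3. How large could the inflation be?** The documents give no frequency for such events. If r is the per-exchange rate of true during/post reactions and q the share of exchanges with a same-day, pre-exchange, procedure-related event, and the two are independent, the counted rate is 1 − (1 − r)(1 − q). Purely as illustration, take r from the 12% and 7% in Protocol 5.2.2.7. That section does not state that these are per-session rates, so using them this way is an assumption. Take q from 0.5% to 5%, also assumed:

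- r = 7%: from 1 − 0.93 × 0.995 = 7.47% to 1 − 0.93 × 0.95 = 11.65%.
- r = 12%: from 1 − 0.88 × 0.995 = 12.44% to 1 − 0.88 × 0.95 = 16.40%.

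This shows only how the error scales with q. It is not an estimate.

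**4. Where is the product wrong?** Apply the SAP product rules to the 18 sessions and mark each session whose product differs from the one before.

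- Arms 1 and 2: LVPE1 (albumin 5% to Flebogamma), LVPE5 and LVPE9 (albumin 20% to Flebogamma), and LVPE2, LVPE6 and LVPE10 (Flebogamma to albumin 20%). That is 6 of 17 transitions, three into Flebogamma and three out of it.
- Arm 3: LVPE1 only (albumin 5% to albumin 20%), 1 of 17.
- FPE1, all active arms: albumin 5% is charged before any product was given. Protocol 6.2.1 allows the baseline lumbar puncture on that day, so a pre-exchange event there is possible.
- FPE2–6 and the remaining LVPEs: product unaffected.

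A further mismatch comes from fixing product by visit number. SAP 7.2.1 summarises whether IVIG was infused and the dose given, and SAP 7.2.2 takes as denominator the exchanges performed with each product. If an IVIG dose is skipped or moved and the denominator follows the actual infusion, the numerator still follows the schedule.

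**The case against.** The same-day sentence sits in the paragraph on deriving product. SAP 7.2.1 has no linking rule, and the per-exchange text in 7.2.2 refers to onset time and the most recent exchange. A programmer could read that as the previous session for an event timed before today's, and the 72-hour limit would then exclude it. This stands as an ambiguity. But the same-day sentence is unqualified and is the only linking rule given, so the literal reading is the one to correct.

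Exposure is also narrow, and this stands in full. Only events possibly related to the procedure enter the primary criterion, and the per-exchange related-AE analysis drops events with missing relationship. The pre-session questions cover the time since the last visit or exchange, and the SAE guidance in Protocol Appendix 4 dates an event from first symptoms or from meeting a seriousness criterion, whichever is earlier. An event that began on an earlier day is untouched. A coagulation result that postpones the session under Protocol 5.2.1 leaves no exchange on that date. The intermediate visit at weeks 7–8 should capture some events before LVPE1.

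Some stronger readings are tempting but not supported:

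- **That product errors distort the primary safety criterion.** It is not split by product.
- **That the by-product tables are the only separation of IVIG from albumin harms.** Safety is summarised by treatment group, and arms 2 and 3 have the same intensive period and the same half-dose albumin 20% but differ in IVIG at LVPE1, 5 and 9. That comparison does not use the product rule.
- **That events drift between products in one direction.** Three transitions go each way, and they count intervals, not events.
- **That a definite share of related events is misassigned.** No document supplies one.

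**Conclusion.** The point holds as a minor one. As written, the SAP can count a procedure-related finding that began before an exchange as a reaction to it. For exchanges within window this can only raise the primary safety percentage, because the previous exchange is at least about 120 hours back. The size cannot be estimated from the documents. Separately, in the by-product tables, same-day pre-exchange events take the wrong product at six sessions in arms 1 and 2 and one in arm 3, and take a product not yet given at FPE1.

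This rests on three assumptions: the same-day rule in 7.2.2 also governs the criterion in 7.2.1; onset and exchange start times are usually recorded; and exchanges take place within their windows. Calling the earlier product the right one follows the SAP's own most-recent-exchange convention and is not a causal claim.

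The severity is limited because SAP 9.1.5 and 9.2.3 make all safety analyses descriptive, and because the error in the primary criterion overstates reactions and does not hide them. In the by-product tables it can move an event away from IVIG as well as towards it.

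**What to change.** Amend SAP 7.2.2 and refer to it from 7.2.1:

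1. Assume during/post exchange for a same-day event only when the onset time or the exchange start time is missing.
2. Otherwise link an event with onset before the exchange start to the previous exchange and its product, or classify it as pre-treatment if it precedes FPE1.
3. Apply the 72-hour window to the linked exchange, with a lower limit at the start of that exchange and the present upper limit at its end plus 72 hours.
4. Derive product from the recorded infusion at that exchange, not from the visit number, and count the by-product denominators the same way.

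The cost is a few lines of SAP text and slightly more derivation programming. It needs no new data.

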5.4 TREATMENT MISALLOCATIONS

For subjects with errors in treatment allocation, they will be reported for efficacy and safety analyses as follows:

If a subject was:

- Randomized but not treated (treatment is defined as attending post baseline study visits), then they are by definition excluded from the efficacy and safety analyses as actual treatment is missing.
- Treated but not randomized, then by definition they will be excluded from the efficacy analyses since randomized treatment is missing, but will be reported under the treatment they actually received for all safety analyses.
- Randomized but took incorrect treatment, then they will be reported under their randomized treatment group for all efficacy analyses, but will be reported under the treatment they actually received for all safety analyses.

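### The adverse-event tables by product take the product from arm and visit number, not from what was infused, so an event after a low-volume exchange without its infusion is credited to a product not given at that session

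*SAP*

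**What the plan says.** SAP 7.2.2 plans two outputs by product (albumin 5%, albumin 20%, Flebogamma DIF 5%): related events by system organ class, preferred term and product, and an analysis of adverse events per plasma exchange by product.

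The link runs through the session: "The relationship to the product will be derived from the most recent plasma exchange". For an event dated on the day of an exchange, "it is assumed that the AE is during/post exchange, i.e. the AE will be associated to this PE". The product of the session is then fixed by the schedule. FPE1 to FPE6 are albumin 5%. At LVPE1, LVPE5 and LVPE9, "for the full albumin + IGIV and the half albumin + IVIG treatment arm, the product will be flebogamma DIF 5" per cent, while the albumin-only arm is albumin 20%. "For all other LVPEs, the product will be albumin 20" per cent. None of these rules depends on anything having been infused.

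For the per-exchange analysis by product: "The denominator for this analysis is the number of performed plasma exchanges with the specific products".

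SAP 7.2.1 summarises, for exactly the three IVIG visits in the two IVIG arms, a flag listed as "IVIG infused (yes/no"), the theoretical and infused doses, and "Ratio infused dose /theoretical dose". For all low-volume exchanges it summarises the type of replacement fluid and the volume infused.

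**The concern.** In the maintenance period the product follows plasma removal. Protocol 5.1.3 places both albumin 20% and Flebogamma at the end of the plasmapheresis, and Appendix 3b describes IVIG given off the Aurora instrument through a separate pump. A low-volume exchange can therefore be performed, or stopped during removal, with no product given. The yes/no flag and the dose ratio in SAP 7.2.1 show that the plan allows for this.

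Under the SAP 7.2.2 rule, an event tied to such a session still counts for Flebogamma or albumin 20%. The denominator wording does not say whether scheduled or actual product is meant. If it means actual product, the session can add an event to the numerator without adding an exchange to the denominator. Two programmers could produce different tables from the same text.

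These tables are where the SAP separates the tolerability of IVIG from that of albumin, and safety of the combination is a stated secondary objective.

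**Working it through.** The documents give no figure for this rule, so there is nothing to reproduce. The check traces the rule and then sizes its effect under stated assumptions.

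**Sessions covered.** Planned enrolment is 364, randomised 1:1:1:1, so 364 / 4 = 91 per arm. Protocol 6.2.4 schedules three IVIG sessions per patient in two arms: 2 × 91 × 3 = 546. All active low-volume sessions number 3 × 91 × 12 = 3,276, leaving 3,276 − 546 = 2,730 scheduled as albumin 20%. These are upper limits, because they assume that every enrolled patient attends every session.

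**Reported rate.** Let *m* be the share of IVIG-scheduled sessions performed without IVIG, *r1* the event rate in sessions with IVIG (the rate the table should show), and *r0* the event rate in sessions without it. The numerator under the SAP rule includes both kinds of session.

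- Denominator by schedule: reported = (1 − m)·r1 + m·r0, so the bias is m·(r0 − r1). It is negative, zero or positive as r0 is below, equal to or above r1.
- Denominator by actual product: reported = r1 + [m / (1 − m)]·r0, so the bias is never negative.

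**Numbers.** The documents give none of *m*, *r0* or *r1*. With r1 = 10% assumed:

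| m (sessions of 546) | r0 | Schedule denominator | Actual-product denominator |
|---|---|---|---|
| 2% (about 11) | 3% | 9.86% | 10.06% |
| 2% | 50% | 10.80% | 11.02% |
| 5% (about 27) | 3% | 9.65% | 10.16% |
| 5% | 50% | 12.00% | 12.63% |
| 20% (about 109) | 3% | 8.60% | 10.75% |
| 20% | 50% | 18.00% | 22.50% |

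For the third row: 0.95 × 10% + 0.05 × 3% = 9.65%, and 10% + (0.05 / 0.95) × 3% = 10.16%. For the fourth: 0.95 × 10% + 0.05 × 50% = 12.0%, and 10% + (0.05 / 0.95) × 50% = 12.63%.

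If the product is taken from the infusion record in both numerator and denominator, the rate is r1 whatever *m* is.

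**Onset window.** The 72-hour limit in SAP 7.2.2 is attached to the per-exchange analysis of related events. The by-product sentence follows in the same paragraph and does not repeat it. The window matters because time to the next exchange differs by product. On the Appendix 8 schedule it averages (5 × 7 + 21) / 6 = 9.3 days after a full exchange and 28 days after LVPE1, LVPE5 or LVPE9.

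**The case against.** The strongest reply is that investigator causality screens these events. SAP 7.2.2 drops events recorded as unrelated to the product from the related-event table, and it plans a further table by product, procedure or both. A reaction during plasma removal could be recorded as procedure-only. This narrows the problem but does not remove it. A relationship recorded as unlikely, or missing, counts as related in the summary tables, and the per-exchange sentence by product speaks of adverse events without limiting them to related ones.

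The scope is also limited. If a low-volume exchange did not take place, the event goes to the last exchange that did, so only exchanges performed without infusion matter. Incomplete exchanges are listed with reasons, so some of these sessions can be traced. All safety analyses are descriptive.

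Four stronger readings are tempting, and the documents do not support them:

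- *The rule always inflates the Flebogamma rate.* If every non-infused session had an event, then at m = 5% the rate would be 14.5% by schedule (9.5% + 5%) or 15.3% by actual product (10% + 0.05 / 0.95). Nothing in the documents supports that assumption, and uneventful missed infusions dilute the rate on a scheduled denominator.
- *The rule breaches SAP 5.4.* The sentence "will be reported under the treatment they actually received for all safety analyses" concerns subjects with errors in treatment allocation and sets no rule for single sessions.
- *No onset window applies by product.* The position of the sentence suggests that the 72-hour limit carries over. This is an ambiguity to close.
- *Full exchanges have the same gap between removal and product.* Protocol 5.1.3 replaces plasma with albumin 5% during the full exchange.

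**Conclusion.** The point stands for low-volume exchanges performed without their scheduled infusion. Followed as written, SAP 7.2.2 credits the events of such sessions to Flebogamma or albumin 20%, and nothing in the protocol or SAP overrides the rule.

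The size cannot be known from the documents. The direction depends on a denominator that the SAP leaves open: only upward with actual product, either way with the schedule. At low frequencies of missed infusion and ordinary event rates the effect is negligible. It becomes material if missed infusions are common or happen because of reactions.

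Only the descriptive by-product tables are affected. Efficacy does not use the product, and neither does the primary safety criterion, the percentage of exchanges with a related event. The change is worth making because the required data are already collected and the present wording can yield different tables.

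**What to change.** Amend the product derivation in SAP 7.2.2 as follows:

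1. Take the product from what was recorded as infused at the most recent performed exchange: Flebogamma if IVIG was infused and the infused dose exceeds 0; albumin if the replacement fluid infused exceeds 0.
2. Put exchanges with nothing infused in a separate category, no product infused. Leave the investigator's CRF causality unchanged, so that the category does not reclassify an event as procedure-only.
3. Where onset time is recorded, do not assign to a product an event that began before that session's low-volume infusion started. Step 1 alone would still charge Flebogamma with a reaction during removal when IVIG was given later the same day.
4. Build numerator and denominator from the same infusion record.
5. State that the 72-hour window of the preceding per-exchange analysis also applies by product.

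The cost is SAP wording, a different source variable and one extra table category. No new data are needed.

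### SAP 7.2.2 counts adverse events with missing causality as related per patient but drops them per exchange, and the primary safety criterion has no missing-data rule of its own

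*SAP*

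**What the plan says.** The primary safety criterion (SAP 7.2, Protocol 8.3) is the percentage of plasma exchanges followed by at least one possibly procedure-related adverse event. SAP 7.2.1 adds the time limit: "Only adverse events with an onset no later than 72 hours after the end of the plasma exchanges" count. It says nothing about events with missing causality or missing clock times.

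SAP 7.2.2 has two families of related-event tables.

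- **Per patient.** "Treatment-related adverse event summaries will include adverse events with missing relationship to study drug". The list of what counts as related ends with "or if relationship is missing".
- **Per exchange** (full exchanges, by access route, and low-volume exchanges). The window is restated: "only AEs with an onset time no longer than 72 hours after the end of the most recent plasma exchange will be considered". If the onset time or the end time of the exchange or infusion is missing, "the start date of the AE must be within 2 days after the date of the most recent plasma exchange". Then comes "Adverse events with missing relationship will not be considered in this analysis".

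The same section deals with missing seriousness: "Adverse events missing the flag indicating serious will be excluded from the summary of serious adverse events".

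**The concern.** A missing causality entry is treated cautiously in one set of tables and discarded in the other, within one section and with no reason given. The reversal falls on the exchange-level count, which is the unit of the primary safety criterion. Because 7.2.1 has no rule of its own, either the 7.2.2 exclusion is carried over, and unassessed events leave the criterion, or the programmer has to choose.

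The other two rules also act in the less cautious direction. An event with no seriousness flag cannot enter the SAE summary. The date fallback does not reproduce the window it replaces. It is also triggered by a missing exchange end time, so one gap in a procedure record affects every event after that exchange. At stake are the related-reaction rate per exchange, the SAE count, and the reader's ability to reconcile the two families of tables.

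**Working it through.** There is no stated figure to reproduce, so the first step is to set the rules side by side.

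| Gap in the record | Place | Handling | Effect on reported count |
|---|---|---|---|
| Relationship, patient tables | SAP 7.2.2 | counted as related | raises |
| Relationship, per-exchange tables | SAP 7.2.2 | event dropped | lowers |
| Relationship, primary criterion | SAP 7.2.1 | no rule | open |
| Seriousness flag | SAP 7.2.2 | left out of SAE summary | lowers |
| Clock time | SAP 7.2.2 | calendar-date fallback | shortens the post-exchange window |
| Event dated on the exchange day | SAP 7.2.2 | attached to that exchange | raises |
| Partial start date in the month or year treatment began | SAP 8 | set to treatment start unless a full stop date precedes it | raises |

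**Date fallback.** Let the exchange end at clock hour t on day D. The 72-hour window closes at hour t on day D+3. The fallback admits dates D, D+1 and D+2, so after the end of the exchange it covers (24 − t) + 48 = 72 − t hours. Extending it to D+3 would cover 96 − t hours.

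| End of exchange (assumed) | Covered now, 72 − t | Share of window lost, t/72 | Covered through day 3, 96 − t |
|---|---|---|---|
| 09:00 | 63 h | 12.5% | 87 h |
| 12:00 | 60 h | 16.7% | 84 h |
| 18:00 | 54 h | 25.0% | 78 h |

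The limits are 72 h (t = 0) and 48 h (t = 24). All the lost time lies on day D+3. The share of window lost equals the share of events lost only if onset is uniform over 72 hours; with early onset, fewer events are lost. The fallback also admits events from before the exchange on day D.

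**Missing causality, illustration only.** The documents give no share m of events with missing causality, so m is assumed. If each affected exchange has one related event and missingness does not depend on relatedness, a true per-exchange rate p is reported as p(1 − m). The 7% and 12% rates are borrowed from the plasma-exchange review in Protocol 5.2.2.7.

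| m | p = 7% | p = 12% |
|---|---|---|
| 1% | 6.93% | 11.88% |
| 5% | 6.65% | 11.40% |
| 10% | 6.30% | 10.80% |

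The patient-level rule moves the other way. Suppose 37.5% of events are truly related. Counting missing as related gives 0.375 + 0.625m; dropping them from the related count gives 0.375(1 − m). For m = 1%, 5% and 10% these are 38.1% against 37.1%, 40.6% against 35.6%, and 43.8% against 33.8%. The gap is m itself.

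**The case against.** Several points on the other side stand.

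- **Missing entries should be few.** Protocol 9.1.1 makes time of appearance, seriousness and causality part of the minimum record for every event. SAEs also go through a separate 24-hour report (Protocol 9.2), whose completion guide in Appendix 4 requires at least one seriousness criterion and an entry for relationship to study drug. An unflagged SAE should be rare and detectable. These requirements do not cover exchange end times.
- **There is a backstop.** SAP 7.2.1 also reports the per-exchange percentage irrespective of causality, which a missing causality entry cannot change. It does not repair the related-event criterion or the SAE summary.
- **The two families of tables differ by design.** The patient tables ignore the 72-hour limit and count patients. The per-exchange tables apply the limit and count exchanges. They would not agree even with complete data, so only part of any disagreement comes from the missing-data rules.
- **No inference depends on this.** All safety analyses are descriptive (SAP 9.1.5 and 9.2.3).
- **Neither date rule reproduces 72 hours.** For exchanges ending between 09:00 and 18:00, a fallback through day 3 covers 78 to 87 hours, so making it the main rule would admit events outside the definition in 7.2.1.

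A reader might also try to size the effect by applying 7% to 12% to every planned active exchange. The documents do not support that. The rates come from Guillain-Barré patients, with no denominator stated for the percentages. Protocol 5.2.2.7 expects a much lower rate in low-volume exchanges, which are 12 of the 18 planned per patient. Events that occur immediately are also not lost to the date rule.

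**Conclusion.** The point holds as an internal inconsistency plus an omission. SAP 7.2.2 sends the same gap in opposite directions depending on the table, and the per-exchange direction is the less cautious one. SAP 7.2.1 gives the primary safety criterion no rule. The seriousness rule is also anti-conservative, and the date fallback falls short of the stated window by up to 24 hours.

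Three stronger readings go beyond the text. A reader might infer that incomplete records always reduce reported harm. The patient-level rule, the same-day rule and the partial-date rule in SAP 8 can all raise counts. A reader might infer that the 7.2.2 exclusions already govern the primary criterion. They are written for the 7.2.2 tables, and carrying them over is reasonable but not stated. A reader might take the fallback as a flat 48-hour cut. That is only its lower limit.

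The effect is unknown and probably small. Under the assumptions above, the proportional fall in the per-exchange related rate equals the share of events with missing causality. The change is still worth making: the SAP foresees these gaps by writing rules for them, and its own patient-level rule already supplies the cautious answer.

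**What to change.** Amend SAP 7.2.1 and 7.2.2 before database lock.

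1. State the missing-data rule for the primary safety criterion in 7.2.1 and refer to it from 7.2.2. Count events with missing relationship as related in the per-exchange analysis, as the patient tables already do. Say which relationship entry is meant, since the patient-level rule is worded for study drug and the criterion concerns the procedure.
2. Count events with a missing seriousness flag as serious, or show a worst-case SAE count beside the planned one.
3. For missing clock times, add a sensitivity count that runs through day 3, with a note that it can admit events beyond 72 hours.
4. Report the number of events affected by each rule.

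The cost is a few sentences and three programming conditions. Reported rates may rise slightly.
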